13.4.5. SLE Allowable and Prohibited Medication Categories

Medication Category	Rule
Anti-malarials	Set to "ANTIMALARIALS" if the preferred term begins with "QUINACRINE", "QUININE", "HYDROXYCHLOROQUINE", "MEPACRINE", or "CHLOROQUINE" AND the route of administration is not 'TOPICAL', 'VAGINAL', 'CONJUNCTIVAL', 'INTRANASAL', 'INHALATION', 'INTRA-OCULAR', 'INTRATRACHEAL', 'EPIDURAL', 'INTRA-ARTICULAR', or 'OTHER'.
Steroids	Set to 'STEROIDS' if at least one associated ATC code (ATCCD1 – ATCCD6) begins with 'H02' AND Route of administration is "INTRADERMAL", "INTRAMUSCULAR", "BUCCAL", "PARENTERAL", "INTRAVENOUS", "ORAL", "SUBCUTANEOUS", or "INTRA-ARTICULAR".
Immunosuppressants	Set to 'IMMUNOSUPPRESSANTS' if at least one associated ATC code (ATCCD1 – ATCCD6) begins with 'L04A' or the preferred term begins with "CYCLOPHOSPHAMIDE" (oral) or "MERCAPTOPURINE" (oral route) AND route of administration is not "TOPICAL" or "OPHTHAMLIC" AND not classified above as "ANTIMALARIALS".
NSAIDs	Set to NSAIDs if at least one associated ATC code (ATCCD1 – ATCCD6) begins with 'M01A'. Glucosamine and Chondroitin are not considered NSAIDs
Aspirin	Set to "ASPIRIN" if CMDECOD contains "ACETYLSALICYLIC ACID" or "ACETYLSALICYLATE LYSINE".
Prohibited	Set to "PROHIBITED" if at least one associated ATC code (ATCCD1 – ATCCD6) begins with 'L04AB' or 'V98' or if any of the following conditions are met, if CMDECOD equals "INVESTIGATIONAL DRUG", "ADALIMUMAB", "ETANERCEPT", "INFLIXIMAB", "CERTILIZUMAB", "TOCILIZUMAB", "GOLIMUMAB", "RITUXIMAB", "ABATACEPT", "ANAKINRA", "CANAKINUMAB", "USTEKINUMAB", "BRODALUMAB", "SECUKINUMAB", "IXEKIZUMAB", "EPRATUZUMAB", "TABALUMAB", "ATACICEPT", "IMMUNOGLOBULIN" (IV route), "CYCLOPHOSPHAMIDE" (IV route) or "LEUKAPHERSIS".
	No programmatic checks are carried out for live vaccines, as this is carried out instream.

13.4.6. Coronavirus Disease 2019 (COVID-19) Environment Onset Date

A COVID-19 environment onset date has been defined by GlaxoSmithKline for each Country as:

Country	COVID-19 Environment Onset Date
Argentina	10/FEB/2020
Germany	10/FEB/2020
Japan	28/FEB/2020
Mexico	10/FEB/2020
Netherlands	10/FEB/2020
Spain	10/FEB/2020
United States	10/FEB/2020

This represents the best estimate of the outbreak of COVID-19 within each Country at this time.

13.5. Appendix 5: Reporting Standards for Missing Data

13.5.1. Premature Withdrawals

Element Reporting Detail	
 completed Part A if all visits up to Week 1 All available data from participants who wand all available planned data will be included the otherwise specified. 	p to and including the Week 52 visit. In the optional Part B will be considered to have

13.5.2. Handling of Missing Data

Element	Reporting Detail	
General	Missing data occurs when any requested data is not provided, leading to blank fields on the collection instrument:	
	 These data will be indicated by the use of a "blank" in subject listing displays. Unless all data for a specific visit are missing in which case the data is excluded from the table. 	
	 Answers such as "Not applicable" and "Not evaluable" are not considered to be missing data and should be displayed as such. 	
Outliers	Any participants excluded from the summaries will be documented along with the reason for exclusion in the clinical study report.	

13.5.2.1. Handling of Missing and Partial Dates

Element	Reporting Detail
General	Partial dates will be displayed as captured in subject listing displays.
Adverse Events	The eCRF does not allow for the possibility of partial dates.
Concomitant Medications/ Medical History	 Missing concomitant medication start date (CMSTDT) is imputed as treatment start date (TRTSDT) unless: concomitant medication end date (CMENDT) is prior to treatment start date (TRTSDT), whether CMENDT is complete (DD/MM/YY) or partial (some combination of CMENDT day, month or year imputed) OR The month or month and year of the partial CMSTDT are different from the month and/or year of TRTSDT OR "Taken prior to study?" is checked. If any of the above conditions are met then CMSTDT is imputed with Jan for missing month and 01 for missing day, whatever is applicable. The recorded partial date will be displayed in listings. Completely missing end dates for concomitant medications (CMENDT) will not be imputed, and the medication will be considered ongoing. If month and year are

CONFIDENTIAL

Element	Reporting Detail
	present, then set to the earlier of (last contact date and last day of that month). If only
	year present, then set to the earlier of (31DEC of the year and last contact date).

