7.2.2.1. Baseline Prednisone Dose

At baseline, the average daily prednisone dose is the sum of all prednisone doses over 7 consecutive days up to, but not including Day 1, divided by 7.

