7.2.2.3. Average Daily Prednisone Dose at the Visit

While on study, the average daily prednisone dose at the visit is the sum of all prednisone doses over 7 consecutive days up to and including the day of interest, divided by 7. Days on which a subject does not have prednisone use recorded will be considered as 0 mg for the day in the calculation of average daily prednisone dose.

The average daily prednisone equivalent dose will be calculated for each scheduled visit. For subjects who withdraw from the study, the early withdrawal visit will only be presented if it slots into a scheduled visit (see Section 13.1.1).

7.2.2.4. Any Decrease from Baseline in Prednisone among Subjects using Prednisone at Baseline (Observed)

The number and percentage of subjects having any decrease compared to baseline among subjects using prednisone at baseline will be presented by visit [T2.05]. These summaries will be based on the average daily prednisone dose at the visit, as calculated in Section 7.2.2.3. No statistical tests will be performed.

A line graph will be produced by visit for the percentage of subjects (±SE) having any decrease in prednisone compared to baseline among subjects using prednisone at baseline [F2.02].

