7.2.2.5. Any Increase from Baseline in Prednisone (Observed)

The number and percentage of subjects having any increase compared to baseline will be presented by visit [T2.06]. These summaries will be based on the average daily prednisone dose at the visit, as calculated in Section 7.2.2.3. No statistical tests will be performed.

A line graph will be produced by visit for the percentage of subjects (\pm SE) having any increase in prednisone compared to baseline [F2.03].

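### Partial steroid stop dates are pushed to month-end or 31 December with no overlap rule, so a step-down to a lower non-zero dose can be scored as a prednisone increase

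*SAP*

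**What the plan says.** SAP 13.5.2.1 gives three rules for medication end dates. With month and year known, the date is "then set to the earlier of (last contact date and last day of that month". With only the year known, it is "then set to the earlier of (31DEC of the year and last contact date". A completely missing end date "will not be imputed, and the medication will be considered ongoing". Last contact date is the only cap. For a partial start date in a different month or year from treatment start, a missing day becomes the 1st and a missing month becomes January.

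SAP 7.2.2 converts all corticosteroids to a prednisone-equivalent daily dose. Baseline (7.2.2.1) is the "sum of all prednisone doses over 7 consecutive days up to, but not including Day 1, divided by 7". The dose at a visit (7.2.2.3) is "the sum of all prednisone doses over 7 consecutive days up to and including the day of interest, divided by 7". SAP 13.4.4 covers conversion factors, routes, and the need for a dose and frequency. It does not say what to do when two records of the same steroid overlap.

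SAP 7.2.2.4 (T2.05, F2.02) counts any decrease among baseline prednisone users. For increases, SAP 7.2.2.5 (T2.06, F2.03) says: "The number and percentage of subjects having any increase compared to baseline will be presented by visit". Neither has a minimum size. Protocol 6.5.1.2.1 lets investigators raise or lower systemic steroids from Day 1, so step-downs are expected.

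**The concern.** Stretching each record to its longest possible length is sensible when the question is whether a drug was concomitant. It does not suit a daily dose. When a dose changes, one record ends and another begins. If the first has a partial stop date, it is carried past the start of the second, and both doses are summed for the same days. Because T2.05 and T2.06 use only the sign of the change, the double count can turn a decrease into an increase. There is no control arm in which the same error would show up for comparison, and steroid change is one of only a few efficacy summaries planned.

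**Working it through.** The plan states no figure on this point, so the rules were applied as written. Doses and dates below are assumptions for illustration, not trial data.

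**Condition for a false increase.** Let a be the baseline dose and b the new dose, with r = b/a below 1. In the 7-day window ending on the visit, let n be the days on or after the cut and q the days after the imputed stop.

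- True mean = [a(7 − n) + b·n]/7, which is below a.
- SAP mean = [a(7 − q) + b·n]/7.
- The SAP mean exceeds a when r·n > q.

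For a window wholly after the cut (n = 7) and a halved dose, 3.5 > q is needed, so the overlap must cover at least 4 of the 7 days. For a cut to zero (r = 0) the condition can never hold.

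**Worked records.** Day 1 is 1 February 2021, so Day 57 is 29 March. The dose changes on 10 March and the old stop is recorded as March 2021, hence imputed to 31 March. The Day 57 window is 23 to 29 March, so n = 7, q = 0 and the SAP mean is a + b.

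| Change (mg/day) | Baseline | True Day 57 | SAP Day 57 | Scored as |
|---|---|---|---|---|
| 20 to 15 | 20 | 15 | 35 | increase |
| 20 to 10 | 20 | 10 | 30 | increase |
| 20 to 5 | 20 | 5 | 25 | increase |
| 10 to 7.5 | 10 | 7.5 | 17.5 | increase |
| 20 to 0 | 20 | 0 | 20 | no change (decrease missed) |
| 30 to 20 (complete date), then 15 | 30 | 15 | 35 | increase |
| 40 to 20 (complete date), then 15 | 40 | 15 | 35 | decrease, but overstated dose |

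If only the year is known, the 20 to 10 change reads 30 mg/day at every visit from Day 57 to Day 309.

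**How often, given a partial date.** Assumptions: one cut from the baseline dose on a uniformly random day (Days 2–85 for Part A, 86–365 for Part B); old record missing only its stop day, giving 0 to 29 days of overlap; visits attended on Days 8, 15, 29, 57, 85, 113, 141, 169, 211, 253, 309 and 365; 200,000 simulated cuts per setting.

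| Wrongly scored as increase | Part A cut | Part B cut |
|---|---|---|
| First visit after the cut, dose halved | 69% | 43% |
| First visit, cuts of 75% down to 10% | 64–77% | 38–50% |
| All visits after the cut to Week 52, dose halved | 9% | 12% |

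A month-only overlap lasts under 30 days, so it usually spoils one visit. A version using calendar months gave at least one wrong visit in 73% of halvings in Part A and 51% of halvings at any time to Day 365. With a year-only date (0 to 364 days of overlap), the first visit is wrong in about 94–98% of cuts.

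**Baseline.** A 20 mg/day course on 1–5 March, stop recorded as March, Day 1 on 20 March: the baseline window 13–19 March is filled by the imputed stretch, so baseline is 20 instead of 0. With a constant 5 mg background dose, baseline is 25 instead of 5, and the unchanged 5 mg at Day 29 scores as a decrease. Year-only: a course that ended on 16 January with Day 1 on 1 October gives 20 instead of 0.

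**Effect on a percentage.** One child moves a T2.06 percentage by 1/28 = 3.6 points at that visit. In T2.05 the denominator is baseline prednisone users, whose number is not given, so the shift is at least as large.

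**Check of the fix.** Ending the old record on 9 March, the day before the new one starts, gives 15 mg/day at Day 57 in the first example, a decrease.

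**The case against.** The trigger may be uncommon. Protocol 6.5 asks for start and end dates of every medication, concomitant medications are reviewed at every Part A and B visit, on-treatment visits are at most 8 weeks apart (Days 253, 309 and 365), and SAP 3.2 requires cleaning before the first lock. An on-study change known only to the year is hard to imagine with visits that close. All of this stands, and the documents give no count of partial dates. Yet SAP 13.5.2.1 says the eCRF does not permit partial dates for adverse events and then writes detailed rules for partial medication dates, so the plan expects some.

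The link is also inferred: 13.5.2.1 does not state that imputed dates feed the dose sum. But it is the only end-date rule in the SAP, and 7.2.2 offers no other. If another rule is intended, it needs to be written.

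The stakes are modest. Prednisone is not a protocol endpoint, nothing is tested, and L1.09 and L2.02 would let a careful reader spot a jump. The tables and figures would still be wrong.

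A reader might infer that every taper is scored as an increase. The documents do not support that: complete dates are unaffected, a visit window must meet the overlap, a cut to zero yields at most a missed decrease, and a late step from a much higher baseline can remain a decrease. A reader might also infer that finished courses routinely inflate baseline. Protocol 5.1 and 6.5.1 require a stable SLE regimen for 30 days before Day 1, which leaves mainly short courses for other conditions (exclusion criterion 15 bars only three or more within 90 days) and year-only dates.

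**Conclusion.** The point holds in a limited form. Followed literally, the SAP double-counts steroid dose after a step-down to a non-zero dose whenever the old record has a partial stop date, and a visit inside the overlap can show a true decrease as an increase. Given a month-only date and a halved dose, this affects the first visit after the cut in about 69% of Part A and 43% of Part B cuts, but only about 9% and 12% of all post-cut visits. These figures depend on one cut per child, a random cut day and attended visits. They are conditional on a partial date, and the frequency of partial dates is unknown, so the overall bias in T2.05 and T2.06 cannot be sized. The false-baseline route (also reaching T1.17) is possible but narrow. The primary PK, safety, biomarker and SELENA SLEDAI results are untouched. It should be corrected because a written rule gives a wrong answer and the remedy is nearly free.

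**What to change.** Keep SAP 13.5.2.1 for the prior/concomitant classification. For the prednisone-equivalent calculation only, add to SAP 7.2.2 or 13.4.4:

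- An imputed stop date may not pass the day before the next record of the same steroid starts.
- An imputed start date may not precede the day after the previous record's stop.
- Where both adjoining dates are partial, say which of the two rules is applied first.

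Query all partial systemic-steroid dates before the first database lock.

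Do not go further and assign zero dose to courses with a blank stop date and no use on Day 1. A blank means ongoing, so that would erase true increases begun on study and the new, lower dose after a taper. If a baseline safeguard is wanted, restrict it to courses that started before Day 1, have a partial (not blank) stop date, and have no confirmed use on Day 1.

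The cost is a few lines of text, one derivation step and a targeted query. A few uncertain days of steroid use may be left out, and two records of the same steroid that truly ran together could be cut short unless the query resolves them.

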13.6. Appendix 6: Abbreviations & Trade Marks

13.6.1. Abbreviations

Abbreviation	Description
ADaM	Analysis Data Model
AE	Adverse Event
AESI	Adverse Event of Special Interest
ALT	Alanine amininotransferase
ANA	Anti-nuclear Antibody
Anti-dsDNA	Anti-double-stranded DNA
AST	Aspartate aminotransferase
ATC	Anatomical Therapeutic Chemical
AUC	Area Under the Curve
BLyS	B Lymphocyte Stimulator
BMI	Body Mass Index
C3/C4	Complement Factor C3 and C4
Cavg	Average Concentration
CDISC	Clinical Data Interchange Standards Consortium
CI	Confidence Interval
Cmax	Maximum Concentration
Cmin	Minimum Concentration
CMQ	Customized MedDRA Query
CNS	Central Nervous System
COVID-19	Coronavirus Disease 2019
CPMS	Clinical Pharmacology Modelling & Simulation
CRP	C-reactive Protein
CRF	Case Report Form
CSR	Clinical Study Report
CTCAE	Common Terminology Criteria for Adverse Events
DBL	Database Lock
DP	Decimal Places
dsDNA	Double Stranded Deoxyribonucleic Acid
eCRF	Electronic Case Report Form
ECG	Electrocardiogram
EW	Early Withdrawal
GFR	Glomerular Filtration Rate
GSK	GlaxoSmithKline
HZ	Herpes Zoster
ICE	Intercurrent Events
ICF	Informed Consent Form
IDSL	Integrated Data Standards Library
IgA	Immunoglobulin A
IgG	Immunoglobulin G
IgM	Immunoglobulin M
IMMS	International Modules Management System

Abbreviation	Description
ITT	Intent-To-Treat
IV	Intravenous
IWRS	Interactive Web Response System
KM	Kaplan-Meier
LLN	Lower Limit of Normal
LOQ	Limit of Quantitation
MAP	Modelling and Analysis Platform
MedDRA	Medical Dictionary for Regulatory Activities
NMSC	Non-melanoma skin cancer
NSAID	Nonsteroidal Anti-Inflammatory Drug
OI	Opportunistic Infections
PD	Pharmacodynamic
PDMP	Protocol Deviation Management Plan
PISR	Post-injection systemic reactions
PK	Pharmacokinetic
PopPK	Population PK
PRT	Pharmacokinetics Review Team
PSAP	Program Safety Analysis Plan
PT	Preferred Term
RAP	Reporting & Analysis Plan
RBC	Red Blood Cell
SAC	Statistical Analysis Complete
SAE	Serious Adverse Event
SC	Subcutaneously
SD	Standard Deviation
SDTM	Study Data Tabulation Model
SE	Standard Error
SELENA	Safety of Estrogen in Lupus National Assessment
SLE	Systemic Lupus Erythematosus
SLEDAI	Systemic Lupus Erythematosus Disease Activity Index
SoA	Schedule of Activities
SOC	System Organ Class
SRT	Safety Review Team
TB	Tuberculosis
TFL	Tables, Figures & Listings
ULN	Upper Limit of Normal

13.6.2. Trademarks

Trademarks of the GlaxoSmithKline Group of Companies
BENLYSTA (belimumab)
BLyS
LymphoStat-B

Trademarks not owned by the GlaxoSmithKline Group of Companies
MedDRA
SAS
NONMEM

13.7. Appendix 7: List of Data Displays

13.7.1. Data Display Numbering

RAP generated displays follow the Format AX.YY, where:

A refers to the type of output i.e.

- T = Table
- L = Listing
- F = Figure

X refers to the section i.e.

- 1 = Study population
- 2 = Efficacy
- 3 = Safety
- 4 = Biomarkers
- 5 = Pharmacokinetic

YY is an incremental count with a new number for every output.

13.7.2. Mock Example Shell Referencing

Example displays are provided in the document 'TFL Mock Outputs MID200908'.

13.7.3. Deliverables

Delivery	Description
Primary SAC	Primary Statistical Analysis Complete

14. ATTACHMENTS

14.1. Attachment 1: AESI Preferred Term Definitions

The AESI definitions under the current version of MedDRA at the time of reporting will be found via the following IMMS pathname:

/Study File/GSK1550188/ Project/Meta Analysis/PSAP/
